9.4 Variable Definitions

9.4.1 Exposure Definition

Exposure to oral cladribine or fingolimod will be documented based on the date of the first prescription or record of treatment in the selected data sources. In the Nordic countries, the MS drug exposure data will be primarily collected from the MS registers and can be complemented with the data from the Prescription registers. As the objective of this observational study is to evaluate long-term safety in patients newly treated with oral cladribine or fingolimod in routine clinical practice, there will be no restriction on possible concomitant treatments in the enrolled patients. Concomitant treatments will be recorded as described above in Section 9.3. In the Nordic countries, data on concomitant medications will be collected both from MS registers and Prescription registers.

For both cohorts, data regarding unit dose, frequency of administration, duration of therapy (start and stop dates), and dose adjustments will be collected, if feasible. Continuation and subsequent changes in oral cladribine and fingolimod treatments will be based on the data as captured in the data sources.

Primary exposure definition (Intention-to-treat)

The intention-to-treat exposure will be classified in the following mutually exclusive categories:

- Oral cladribine at enrolment;
- Fingolimod at enrolment;

and is defined as the first study drug prescribed at enrolment, with at least one day of treatment, regardless of subsequent treatment discontinuation or switch.

As-treated exposure definition

The as-treated exposure definition is defined as time-dependent exposure indicating on-going treatment with the following mutually exclusive categories:

- Current exposure to oral cladribine;
- Current exposure to fingolimod

At treatment switch from oral cladribine to fingolimod and vice versa, current exposure will be extended by a washout period of 6 months for the discontinued treatment after which the exposure to the newly initiated treatment will start.

Time since last dose received

Treatment with oral cladribine and fingolimod will be classified in the following mutually exclusive categories of exposure:

• Current use: for ongoing treatment;

• Recent use: Days 1-365 after date of last dose received;

• Past use: more than 1 year after date of last dose received.

9.4.2 Outcome Definitions

Malignancy: Any occurrence of malignant neoplasms during the study period. These will be grouped and classified by type. Malignancies will include all pathologically confirmed solid tumors (excluding non-melanoma skin cancer) and hematological malignancies, as the primary outcome for all malignancies-related analyses. Benign tumors will not be collected. The pre-defined groups are the following:

- Any malignancies excluding non-melanoma skin cancer (NMSC) (primary)
- Any malignancies including NMSC
- Solid tumors only
- Hematological tumors only

Severe infections:

The following categories will be investigated:

- Tuberculosis
- PML
- Opportunistic infections (excluding herpetic infections, tuberculosis, and PML): defined as an invasive infection caused by microorganisms that are normally non-pathogenic or rarely pathogenic in individuals with normal immune function or cause an infection of a type or severity not seen in the normal host.
- Other severe infections

All bacterial, viral, fungal, parasitic and protozoal infections that occur during the study period and regardless of the duration of infection will be recorded. The duration of infections will be the difference between start date and recovery date as reported by the treating physician. Patients may contribute for more than one episode to this analysis if, after resolution as defined, another infection occurs.

An infection will be considered severe if it leads to a significant impairment of functioning, i.e., the subject is unable to carry out usual activities. This definition includes serious and non-serious infections, in line with the definition used in the RMP of oral cladribine. An infection is considered serious if it fulfills at least one of the following seriousness criteria: results in death, is life-threatening, requires in-patient hospitalization or prolongation of existing hospitalization, results in persistent or significant disability/incapacity, is a congenital anomaly/birth defect, or is otherwise considered as medically important.

As the availability of data related to certain infections may vary among the databases, detailed operational definitions for the identification of severe and opportunistic infections in different disease coding systems used by data sources of the study will be defined in the statistical analysis plan (SAP).

Herpes zoster infections: Regardless of the severity.

Severe lymphopenia: Any occurrence of severe lymphopenia during the study period, classified as Grade ≥ 3 . As per the Common Terminology Criteria for Adverse Events (CTCAE) (V4.03: June 14, 2010) from the National Institutes of Health, the grades of lymphopenia are defined based on laboratory test results that indicate a decrease in number of lymphocytes in a blood sample:

- Grade 3: $<500 200/\text{mm}^3$; $<0.5 0.2 \times 10^9 /\text{L}$
- Grade 4: $<200/\text{mm}^3$: $<0.2 \times 10^9/\text{L}$

Duration of severe lymphopenia: Defined as the interval from the finding of severe lymphopenia until resolution, which is achieving a CTCAE Grade 1 (less than lower limit of normal [LLN] to 0.8×10^9 /L) or normalization (above LLN). Patients may contribute for more than one episode to this analysis if, after resolution as defined, severe lymphopenia occurs. The frequency of lymphocyte counts in patients with severe lymphopenia will be described with special emphasis on the number and timing of lymphocyte counts in relation to oral cladribine dosing.

Treatment interruption: In the oral cladribine cohort, discontinuation will be further defined as stopping the treatment before completion of a treatment course. Discontinuation will be considered temporary if the patient restarts the same or the second treatment course with a delay of up to 6 months. Otherwise, it will be considered permanent. With regards to discontinuation in the fingolimod cohort, it will be considered as temporary discontinuation if the patient restarts fingolimod within 90 days after temporary discontinuation or permanent discontinuation if there are no more records of fingolimod thereafter.

Treatment discontinuation: Treatment discontinuation will be directly recorded by the treating physician and includes any permanent treatment discontinuation (excluding treatment interruption), regardless of the reason for discontinuation. Reasons and dates for discontinuation will also be captured. The treatment stop date will be used to derive the date of treatment discontinuation.

For complete and accurate information, for each of the outcomes defined above, the data collected will include as much detail as possible to corroborate diagnosis, including but not limited, to histopathologic results, and relevant laboratory and imaging results. In addition, the following two outcome categories will be differentiated:

- Reported outcomes: defined as all outcomes reported by physicians with no additional elements to corroborate the diagnosis;
- Confirmed outcomes: defined as all outcomes reported by physicians with any additional elements to corroborate the diagnosis such as histopathology for malignancies.

DMT after cladribine treatment: Sequential use of any DMT (immunosuppressive or immunomodulatory agents) after cladribine treatment in patients who experience a recurrence of the disease activity.

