9.2.5 Frequency of Assessments

No additional visits to the HCP outside of routine practice will be mandated by the protocol. Data collection is conducted according to local routine medical practices and data are captured during routine clinic visits. However, it is expected that data will be collected with a periodicity of at least 6 months over the full study period, based on current practices regarding management of patients with R(R)MS in Europe and other participating countries. Study outcomes (malignancies, severe and/or serious infections, opportunistic infections, lymphocyte counts [if performed according to routine practice], treatment discontinuation and reasons for discontinuation) will be mandatory variables and will be collected during each routine clinical visit. In the data sources with secondary use of data, the data collection will be event-based: the data collected will include only the variables the physician has considered as relevant to be recorded during the visit. All entries recorded in these data sources will be captured. In this real-world setting, the frequency of visits is also expected to be dictated by disease complications or occurrence of AEs.

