Information bias is a distortion in the estimate of association between risk factor and disease that is due to systematic measurement error or misclassification of patients on 1 or more variables, either risk factor or outcome. To preventively minimize this type of bias in the current study, instructions will be provided to all neurologists/physicians in the centers participating through the databases with additional primary data collection. In the data sources with secondary use of data, the data collection is based on routine clinical practice and cannot be influenced in the context of the study.

As the study is non-interventional, only data from clinical routine practice can be obtained. Therefore, some information may be missing or unavailable. As an example, treatment discontinuation and the association of severe lymphopenia and AESIs might be difficult to assess due to low completion and/or heterogeneity of data collection for these outcomes in the participating data sources. In addition, this may be an issue when measuring the duration of lymphopenia. Given that no regular blood tests are requested per protocol, there is a risk to overestimate the duration of lymphopenia. In patients with severe lymphopenia, this risk of bias will probably be minimized as the physician would be expected to perform a closer follow-up with more frequent blood testing. For data sources with additional primary data collection, the data will be entered according to the study protocol and recoding of lymphocyte counts, when performed, is mandatory by the physician. In data sources with secondary use of data, the differences in the recording of lymphocyte counts between different MS treatments and different medical practices will limit the assessment of completeness of recording.

Furthermore, given that oral cladribine is a new drug, the treating physician might pay extra attention and evaluate the patient more frequently (higher number of clinical visits, laboratory testing, etc.), introducing a possible detection bias in comparison to patients treated with fingolimod.

Confounding by indication and/or channeling bias

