Up to 2013, OFSEP was based on an existing cohort of MS patients in France. Today the data are collected from participating centers using the European Database for Multiple Sclerosis (EDMUS) software. OFSEP covers approximately 50% of the total MS population in France and has data for approximately 55,000 patients in total. Of these, 23,000 patients have records after June 2013. OFSEP contains information such as clinical evaluation of patients, the drugs used to treat MS, results of magnetic resonance imaging (MRI) and blood sample analyses (including lymphocyte counts). Access to the data is made directly via an application to the database: the National Coordination Center and the Scientific Board of the database evaluate the applications and the Steering Committee makes the final decision.

NTD - Germany

The NTD database has been established in February 2008, with data collection from 73 practices across Germany. At the moment the database covers approximately 25,000 MS patients. NTD

contains data on the demographic, clinical and socio-economic parameters of the MS patients, recorded at least once per quarter Additional primary data collection can be implemented, and data is entered according to the study protocol. The recoding of all study variables (including lymphocyte counts) is mandatory by the physician ensuring high data quality and completeness. In general, the NTD database has an existing ethical approval, but new studies utilizing the NTD data need a separate ethical approval. The application process is managed by the local principal investigator.

MSDS 3D - Germany, Spain and Switzerland

The MSDS 3D database has been established in 2010. As the database is solely used for conducting specified studies, the number of practices and patients varies by study. For example, in the PANGAEA study studying fingolimod users across Germany recruited approximately 4,000 RRMS patients from approximately 500 neurological centers. MSDS 3D contains information such as clinical evaluation of patients, the drugs used to treat MS and results of MRI. Patient-reported outcomes are also available. Additional primary data collection can be implemented, and data is entered according to the study protocol. The recoding of all study variables (including lymphocyte counts) is mandatory by the physician ensuring high data quality and completeness. The application processes are managed by the local principal investigator.

Italian MS Registry - Italy

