The Italian MS Registry includes data from 57 practices across Italy. This database is managed by the hospital of Bari. The 57 centers cover approximately 80% of the Italian MS population. The database utilizes iMED software, the same as MSBase and contains information such as clinical evaluation of patients, laboratory measurements (including lymphocyte counts) and the drugs used to treat MS.

Finland

Each individual permanently residing in Finland (at least for 1 year) has a unique personal identity number (PID), which carries also information on date of birth and gender. All the data sources listed below include information PIDs that enable linkage of data from different data sources.

Finnish MS data collection system

Finnish MS data collection system is established by a Finnish company called StellarQ. This company acts as a data solution provider for 13 of the 20 Finnish hospital districts and all public healthcare units of these hospital districts treating MS patients utilize their software. The database was established in 2014, but retrospective data collection have been extensively conducted in most hospital districts. The work is still ongoing. The database covers all the major hospital districts treating MS patients in Finland. The database contains extensive and detailed data on the MS patients with additional automatic data extractions from the laboratory databases (including lymphocyte counts) of the contributing hospitals. The data are updated real-time. The hospital districts providing the data to the database are the data holders and permits to obtain access to the data need to be applied separately from each hospital district.

Prescription registers

In Finland, there are 2 different prescription registers: the traditional Prescription register and the new e-Prescription register. The Prescription register is managed by the Social Insurance Institute and contains data since 1994. The e-Prescription register is held by Social Insurance Institute but managed by the National Institute for Health and Welfare. Use of e-prescriptions has been compulsory in public health care since April 2013, and in private health care since January 2015. e-Prescription register is not replacing the traditional Prescription register but they both are further in use. The functions are partly overlapping.

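### The primary malignancy outcome asks for pathological confirmation, but three secondary-use sources are not shown to supply it and their person-time still counts in full

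*Protocol*

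**What the plan says.** Section 9.4.2 of the protocol describes the malignancy outcome in several ways.

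- The definition reads "Malignancies will include all pathologically confirmed solid tumors (excluding non-melanoma skin cancer) and hematological malignancies, as the primary outcome", and applies this to every malignancy analysis.
- The list of groups that follows marks any malignancy excluding non-melanoma skin cancer (NMSC) as primary, with no confirmation condition.
- The end of the section separates two classes: "Reported outcomes: defined as all outcomes reported by physicians with no additional elements to corroborate the diagnosis" and "Confirmed outcomes: defined as all outcomes reported by physicians with any additional elements to corroborate the diagnosis such as histopathology for malignancies". It does not say which class enters the primary analysis.

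Section 9.8.3 (Primary analysis) lists malignancies excluding NMSC, again without a confirmation condition. Section 9.8.2 starts each patient's follow-up at cohort entry, whatever the data source.

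Section 9.1.1 names OFSEP, the Italian MS Registry, MSBase and the Nordic registers as secondary use only. Appendix 2 credits the Nordic cancer registers with tumour morphology or histology, and section 9.5.1 describes linkage by personal identity number for the Nordic countries. For MSBase and the Italian registry, Appendix 2 says that the database "contains information such as clinical evaluation of patients, laboratory measurements (including lymphocyte counts) and the drugs used to treat MS". The OFSEP entry is similar, with MRI results added. For secondary-use sources, section 9.2.5 says that "the data collected will include only the variables the physician has considered as relevant to be recorded during the visit", and section 9.10 says: "In the data sources with secondary use of data, the data collection is based on routine clinical practice and cannot be influenced".

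**The concern.** Malignancy is the outcome for which the CHMP asked for a comparative study (section 7), and it drives the study size (section 9.6). If a case must be pathologically confirmed, a source that cannot confirm adds person-years to the denominator and too few cases to the numerator.

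The protocol describes no way to close that gap in the three clinic-based secondary sources. Collection there cannot be influenced, section 11.5 uses no safety forms for secondary data, and study modules exist only in NTD and MSDS 3D. The limitations in section 9.10 do not discuss cancer ascertainment by source.

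Three results are at stake: the pooled incidence rates and any rate difference would be too low, the ratio would be less precise than Table 4 suggests, and the ratio would be biased if the two cohorts draw differently on these sources.

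**Working it through.** **Inputs from the protocol (section 9.6).** Background rates 0.26 and 0.40 per 100 person-years (PY); 32,907 PY at Year 15; 95% mid-P intervals for the ratio. I take 32,907 as PY per cohort. This fits 4,000 patients, 10 years and about 5% yearly drop-out: 4,000 × (1 + 0.95 + … + 0.95⁹) = 32,101.

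**Inputs not in the protocol, varied over a range.** s = share of person-time in OFSEP, the Italian registry and MSBase; c = fraction of true cancers there that are pathologically confirmed.

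**Step 1: reproduce the plan.** Simulation with conditional mid-P intervals gives, at Year 15:

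- Excluding RR 2 and RR 1.5 at true RR 1: 99.3% and 74.4% for a rate of 0.26 (Table 4: 99%, 74%); 100% and 90.4% for 0.40 (100%, 90%).
- Interval above 1 at true RR 1.3: 45.0% and 62.6% (46%, 62%).
- Table 3, rate difference below 0.5 × background at true RR 1: 89.3% and 98.1% (89%, 98%).

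The stated figures therefore count every cancer in all person-time.

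**Step 2: apply incomplete confirmation, equal in both cohorts.** The fraction of cancers counted is f = 1 − s(1 − c). Expected cases per cohort at 0.26 are E = 32,907 × 0.0026 × f. With s = 50%:

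| c | f | E per cohort | observed rate per 100 PY | exclude RR 1.5 (0.26) | exclude RR 2 (0.26) | detect RR 1.3 (0.26) | exclude RR 1.5 (0.40) |
|---|---|---|---|---|---|---|---|
| 100% | 1.00 | 85.6 | 0.260 | 74% | 99% | 45% | 90% |
| 80% | 0.90 | 77.0 | 0.234 | 71% | 99% | 40% | 87% |
| 50% | 0.75 | 64.2 | 0.195 | 63% | 97% | 36% | 80% |
| 0% | 0.50 | 42.8 | 0.130 | 47% | 88% | 25% | 65% |

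With c = 0, the 74% becomes 62% for s = 25% and 26% for s = 75%.

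Hand check for excluding RR 1.5: Φ(ln 1.5 / √(2/E) − 1.96). E = 77.0 gives Φ(0.56) = 71%; E = 64.2 gives Φ(0.34) = 63%; E = 42.8 gives Φ(−0.08) = 47%.

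**Step 3: rate difference.** It shrinks by the same f. A true RR of 1.3 on 0.26 is an excess of 0.078 per 100 PY. It would be seen as 0.070, 0.059 or 0.039 for f = 0.90, 0.75 or 0.50. Against the fixed 0.13 per 100 PY used in section 9.6, the probability of exclusion at true RR 1 rises from 89% to about 92%, 96% or 99.5%, only because cases go uncounted.

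**Step 4: rate ratio.** With equal f in both cohorts the expected ratio is unchanged. With different source mixes, a true ratio of 1 appears as a crude ratio of [1 − s₁(1 − c)] / [1 − s₀(1 − c)], where s₁ is the cladribine share and s₀ the fingolimod share. For s₁ = 40% and s₀ = 50%:

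- c = 0: 0.60/0.50 = 1.20
- c = 50%: 0.80/0.75 = 1.07
- c = 80%: 0.92/0.90 = 1.02

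With the shares reversed, the values are 0.83, 0.94 and 0.98.

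**The case against.** A reader might infer that OFSEP, the Italian registry and MSBase hold no pathology and would yield few or no countable cancers. The documents do not support that. The Appendix 2 lists are introduced as examples and do not name infections either. Section 9.2.1 says that sources were chosen partly for availability of a minimum dataset. Section 9.4.2 says for every outcome that "the data collected will include as much detail as possible to corroborate diagnosis, including but not limited, to histopathologic results". Zero confirmation is therefore a worst case. At 80% confirmation with half of person-time affected, the loss is only 74% to 71%.

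A reader might also estimate s from the registry sizes in Tables 1 and 2. Those are whole MS populations, not new starters of either drug. MSBase Italy may overlap with the Italian registry, Finland and MSDS 3D have no patient count there, and section 9.10 lets country sizes be adjusted.

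A third tempting inference is a high chance of wrongly ruling out a real excess of 0.13 per 100 PY. That margin belongs to the sizing illustrations in section 9.6. The planned comparison in section 9.8.3 is an adjusted rate ratio, no success margin is set, and equal under-capture leaves the expected ratio unchanged.

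The wording can also be read more mildly: pathological confirmation may apply to solid tumours only, and the statistical analysis plan may say which class enters which model. Neither removes the point. Solid tumours still carry the condition, and the protocol itself states the primary outcome in ways that disagree. Section 9.4.2 defers source-specific definitions to the analysis plan for infections but not for malignancy.

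Finally, a specific case definition has value. Section 9.10 warns that patients on the new drug may be watched more closely, so unconfirmed reports could differ by cohort. That stands, and it is why the fix does not simply replace confirmed with reported cases.

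**Conclusion.** The point holds as an unreconciled case definition combined with a numerator and denominator that may not match. The protocol requires pathology for solid tumours in one place, accepts any corroboration in another and states no condition in a third. It counts all person-time in three sources whose ability to confirm is not shown, and it sizes the study as if every cancer were counted.

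Where confirmation is incomplete, the pooled rates and rate difference are biased towards zero by the factor f. Precision falls below Tables 3 and 4, and the ratio is biased only if source mix differs between cohorts and is not accounted for.

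The size cannot be fixed from the documents. With half of person-time affected, the 74% becomes about 71%, 63% or 47% at 80%, 50% or no confirmation. These values rest on assumed s and c, equal capture in both cohorts (except in Step 4), and 32,907 PY per cohort.

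**What to change.** 1. In sections 9.4.2 and 9.8.3, replace the differing statements with one malignancy case rule. Use one meaning of confirmed, and say which class of case enters the primary analysis.
2. Run the pathologically confirmed analysis with cases and person-time both restricted to sources that can confirm: Nordic cancer-register linkage, NTD, MSDS 3D, and any other source shown to supply pathology.
3. Beside it, report all recorded malignancies excluding NMSC in all sources, stratified or adjusted by data source.
4. State in section 9.6 that Tables 3 and 4 assume complete ascertainment in all person-time and do not apply to the confirmed analysis.

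The cost is wording in three sections and one restricted analysis. The confirmed analysis will be less precise: if half of person-time is excluded, about 16,450 PY × 0.0026 = 42.8 expected cases per cohort remain, and the probability of excluding RR 1.5 is again about 47%, but its rates are no longer diluted. The all-recorded analysis will include some unconfirmed reports and is more open to the detection bias noted in section 9.10, which is a reason to show both.
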